15.12 CAUSALITY ASSESSMENT

The investigator’s assessment of causality must be provided for all adverse events (Serious and Non-Serious); the investigator must record the causal relationship in the CRF, as appropriate, and report such an assessment in accordance with the serious adverse reporting requirements if applicable. An investigator’s causality assessment is the determination of whether there exists a reasonable possibility that the investigational product caused or contributed to an adverse event. If the investigator's causality assessment is "unknown but not related to investigational product", this should be clearly documented on study records.

In addition, if the investigator determines a serious adverse event is associated with study procedures, the investigator must record this causal relationship in the source documents and CRF, as appropriate, and report such an assessment in accordance with the serious adverse event reporting requirements, if applicable.

WHO-UMC Causality Categories

Causality Term	Assessment Criteria
Certain	
 • Event or laboratory test abnormality, with plausible time relationship to drug intake • Cannot be explained by disease or other drugs • Response to withdrawal plausible (pharmacologically, pathologically) • Event definitive pharmacologically or phenomenologically (i.e. an objective and specific medical disorder or a recognized pharmacological phenomenon) • Rechallenge satisfactory, if necessary
Probable / Likely	
 • Event or laboratory test abnormality, with reasonable time relationship to drug intake • Unlikely to be attributed to disease or other drugs • Response to withdrawal clinically reasonable • Rechallenge not required
Possible	
 • Event or laboratory test abnormality, with reasonable time relationship to drug intake • Could also be explained by disease or other drugs • Information on drug withdrawal may be lacking or unclear
Unlikely	
 • Event or laboratory test abnormality, with a time to drug intake that makes a relationship improbable (but not impossible) • Disease or other drugs provide plausible explanations

Causality Term	Assessment Criteria
Conditional/Unclassified	
 • Event or laboratory test abnormality • More data for proper assessment needed, or • Additional data under examination
Unassessable/Unclassified	
 • Report suggesting an adverse reaction • Cannot be judged because information is insufficient or contradictory • Data cannot be supplemented or verified

15.13 EXPOSURE DURING PREGNANCY

For Investigational Products and for marketed products, an exposure during pregnancy (also referred to as Exposure In-Utero [EIU]) occurs if:

1. A female becomes, or is found to be, pregnant either while receiving or having been directly exposed to the Investigational Product (e.g., environmental exposure), or the female becomes, or is found to be, pregnant after discontinuing and/or being directly exposed to the Investigational Product (maternal exposure).
2. A male has been exposed, either due to treatment or environmental, to the Investigational Products prior to or around the time of conception and/or is exposed during his partner's pregnancy (paternal exposure).

If any study subject or study subject's partner becomes or is found to be pregnant during the study subject's treatment with the Investigational Products, the investigator must submit this information to the Sponsor.

This must be done irrespective of whether an adverse event has occurred and within 24 hours of awareness of the pregnancy.

The information submitted should include the anticipated date of delivery.

Follow-up is conducted to obtain pregnancy outcome information on all Exposure during pregnancy reports with an unknown outcome. The investigator will follow the pregnancy until completion or until pregnancy termination (i.e., induced abortion) and then notify the Sponsor of the outcome. The investigator will provide this information as a follow up to the initial Exposure in Utero Pregnant Form. The reason(s) for an induced abortion should be specified.

An EIU report is NOT created when an ectopic pregnancy report is received since this pregnancy is not usually viable. Rather, a serious adverse event case is created with the event of ectopic pregnancy.

If the outcome of the pregnancy meets the criteria for immediate classification as a serious adverse event (i.e., spontaneous abortion, stillbirth, neonatal death, or congenital anomaly [Including that in an aborted fetus, stillbirth or neonatal death]), the investigator should follow the procedures for reporting serious adverse events.

In the case of a live birth, the “normality” of the newborn can be assessed at the time of birth (i.e., no minimum follow-up period of a presumably normal infant is required before an Exposure in Utero Pregnant Form can be completed).

The “normality” of an aborted fetus can be assessed by gross visual inspection, unless pre-abortion test findings are suggestive of a congenital anomaly.

Additional information about pregnancy outcomes that are classified as serious adverse events follows:

1. Spontaneous abortion; includes miscarriage and missed abortion.
2. All neonatal deaths that occur within 1 month of birth should be reported, without regard to causality, as serious adverse events. In addition, any infant death after 1 month that the investigator assesses as possibly related to the exposure during pregnancy to the investigational medication should be reported.

Additional information regarding the exposure during pregnancy may be requested by the investigator. Further follow-up of birth outcomes will be handled on a case-by-case basis (e.g. follow-up on preterm infants to identify developmental delays).

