2 ASSESMENT SCHEDULE

Data to be collected	Study Schedule*					
	V1 screening	V2 Week 0	V3 Week 8	V4 Week 12	V5 Week 24	V6 Week 36
Informed consent	X					
Inclusion/ exclusion criteria	X					
Demographics	X					
Medical/ Surgical history	X					
Concomitant medications	X	X	X	X	X	X
Physical examination	X	X	X	X	X	X
Vital signs	X	X	X	X	X	X
Fibroscan liver stiffness measurement	X				X	X
Fib-4	X		X	X	X	X
Abdominal Ultrasound	X					
Controlled Attenuation Parameter (CAP)	X		X	X	X	X
Serum pregnancy test for females	X		X	X	X	X
PCR	X					
Alpha fetoprotein	X					
HCV RNA	X					
HAV IgM	X					
HBsAg	X					
CBC	X		X	X	X	X
Sodium	X				X	X
Potassium	X				X	X
Serum Fibrinogen	X		X	X	X	X
Liver Profile tests - Albumin, bilirubin, - PT, PTT, INR, - ALT and AST	X		X	X	X	X
Kidney function tests	X				X	X
Lipid Profile	X				X	X
HbA1c	X				X	X
Study drug dispensed		X	X	X	X	
Drug Accountability			X	X	X	X
Adverse Events Serious Adverse Events Hepatic complications		X	X	X	X	X
Study Completion Form						X

* Washout periods at week 13 and week 25.

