9.2 INCLUSION CRITERIA

- 1) Male or female aged between 18 and 65 years.
- 2) Both male and female patients who have childbearing potential must agree to practice an acceptable method of birth control during the study and for at least 6 months after the cessation of treatment; such contraceptive methods must include at least one barrier method.
- 3) Controlled Attenuated Parameter (CAP)-confirmed hepatic steatosis.
- 4) Patients with elevated Liver enzymes (ALT and/or AST) ^[34].
- 5) Liver fibrosis stage F1-F2 as diagnosed by the FibroScan liver stiffness measurement of 5-10 kPa.
- 6) liver condition according the following criteria;
 - Serum albumin > 3 g/dl
 - INR < 2
 - No ascites on ultrasound
 - No documented or suspected hepatic encephalopathy
- 7) Willing to stop any other liver support and hepatoprotective medications throughout study duration.
- 8) Able and willing to provide written informed consent.
- 9) Able and willing to complete all study visits and procedures, including compliance with the requirements and restrictions listed in the consent form.

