10 TREATMENT OF TRIAL PARTICIPANTS

10.1 RANDOMIZATION

Before randomization, fulfillment of the inclusion/exclusion criteria should be assured and the signed informed consent obtained. After that, eligible patients will be randomized in a 1:1:1 allocation ratio, into one of the three treatment groups, to receive either placebo or one of the two doses of Heptex. Randomization will be done using interactive response technology.

Control Arm 1:

Placebo (Rice bran) in 2 capsules size 1, administered PO TID on empty stomach with plenty of water.

Experimental Arm 2:

The contents of one capsule of Heptex is equally distributed and inserted into 2 capsules size 1, administered PO TID on empty stomach with plenty of water.

Experimental Arm 3:

The contents of two capsules of Heptex is equally distributed and inserted into 2 capsules size 1, administered PO TID on empty stomach with plenty of water.

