11 CONCOMITANT MEDICATIONS

Throughout the study, investigators may prescribe any concomitant medications or treatments deemed necessary to provide adequate supportive care except other liver support, hepatoprotective medications and any medications prohibited as per the eligibility criteria. If these are required, the participant will be withdrawn. Any medication, other than the study medication taken during the study will be recorded in the CRF.

Any medication or vaccine (including over-the-counter or prescription medicines, vitamins and/or herbal supplements) that the subject is receiving during participation in the study must be recorded in the electronic case report form. The investigator should review all concomitant medications for any potential interactions. During the Post-Treatment Period, all medications will be collected.

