15.2 REPORTING PERIOD

For serious adverse events, the reporting period to Sponsor or its designated representative begins from the time that the subject provides informed consent, which is obtained prior to the subject's participation in the study, i.e. prior to undergoing any study-related procedures and/or receiving IP, through and till the end of the Follow-Up Period as specified in the study protocol.

Any serious adverse event occurring any time after the reporting period must be promptly reported if a causal relationship to investigational product is SUSPECTED.

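### Section 15.13 requires pregnancy reporting only for the treatment period, short of its own exposure definition and of the 6-month contraception period in inclusion 2; separately, no pregnancy test or eligibility check is scheduled at week 0

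*Protocol*

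**What the plan says.** **After treatment.** Inclusion criterion 2 (Protocol 9.2, repeated in the synopsis) says that men and women able to have children "must agree to practice an acceptable method of birth control during the study and for at least 6 months after the cessation of treatment". Section 15.13 defines exposure during pregnancy. On the maternal side the definition includes a woman who becomes or is found "pregnant after discontinuing and/or being directly exposed to the Investigational Product (maternal exposure"). On the paternal side it includes a man exposed before or around conception. The operative sentence follows: if a patient, or the partner of one, "becomes or is found to be pregnant during the study subject's treatment with the Investigational Products, the investigator must submit this information to the Sponsor". Section 15.13 then sets a 24-hour clock from awareness and requires follow-up to the outcome.

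Two further sections name periods that might be thought to extend this. Section 15.2 runs serious adverse event reporting "through and till the end of the Follow-Up Period as specified in the study protocol". Section 11 says "During the Post-Treatment Period, all medications will be collected".

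**Before the first dose.** Section 9.3 excludes pregnant women (exclusion 1). Section 10.1 says "Before randomization, fulfillment of the inclusion/exclusion criteria should be assured", and section 16.5 places randomization at visit 2, week 0. In the section 2 schedule, the row "Serum pregnancy test for females" is marked at screening and at weeks 8, 12, 24 and 36. The eligibility row is marked at screening only. The week 0 paragraph of section 8.4 lists no laboratory test.

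**The concern.** Within section 15.13 the duty to report is narrower than the definition of what is to be reported. It is also narrower than the period for which the protocol asks patients to avoid pregnancy. An investigator who follows the operative sentence literally could learn of a conception two months after the last dose and find no explicit instruction to report it. Outcome follow-up in 15.13 works through exposure reports, so a pregnancy that is never reported is never followed.

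The week 0 gap is a different problem, at the other end of the trial. The protocol requires eligibility to be settled before randomization, but the visit at which randomization and first dispensing occur has no scheduled step that confirms exclusion 1. A woman who conceives between screening and week 0 could be randomized and dosed, with no scheduled test before week 8.

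Both are patient-safety matters. Neither affects sample size, power or the efficacy analysis.

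**Working it through.** There is no stated figure to reproduce. The check sets the texts side by side and adds calendar arithmetic.

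**1. What each text covers after the last dose**

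| Text | Reach after the last dose |
|---|---|
| Inclusion 2 (9.2) | At least 6 months, both sexes |
| Maternal exposure definition (15.13) | Includes pregnancy after discontinuation, no end date |
| Paternal exposure definition (15.13) | Tied to conception, not to the treatment period |
| Reporting duty (15.13) | Pregnancy that begins or is found during treatment |
| Last pregnancy test, last visit (sections 2 and 8.2) | Week 36, end of study |

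**2. Length of the gap**

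Inputs: 36 weeks from baseline to end of study (8.2); 6 months of contraception after treatment (9.2), taken as about 26 weeks.

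- Contraception period for a patient treated to week 36: week 0 to week 36 + 26 = week 62.
- Reporting duty as worded: week 0 to week 36, plus any pregnancy begun in that time and discovered later.
- Contraception period with no explicit reporting duty for a new conception: 62 − 36 = about 26 weeks.

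**3. Whether another rule closes the gap**

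- Section 15.17 applies the 24-hour timeframe to initial and follow-up exposure reports. It fixes how fast to report, not for how long the duty lasts.
- Section 15.2 requires serious adverse events after the reporting period to be reported if causality is suspected. An uncomplicated pregnancy is not a serious adverse event.
- The Follow-Up Period in 15.2 is not defined. The visit table in 8.2 labels visits 3 to 6 as follow-up and visit 6 as end of study, so the most natural reading ends it at week 36.
- The Post-Treatment Period in section 11 matches no visit in the schedule, and it concerns medications.

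None of these clearly reaches an uncomplicated pregnancy conceived after the last dose.

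**4. Week 0**

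- Pregnancy test: marked at visits 1, 3, 4, 5 and 6; not at visit 2.
- Eligibility check: marked at visit 1 only.
- Randomization and first dispensing: visit 2 (16.5 and section 2).
- Age of the screening test at week 0: no maximum is given.
- Time on drug before the next scheduled test: week 8 − week 0 = 8 weeks.

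**The case against.** The strongest reply is that 15.13 already defines exposure to include pregnancy after discontinuation, and 15.17 attaches the reporting timeframe to exposure cases without limiting them to treatment. On that view a sensible investigator would report a later pregnancy anyway, and the defect is one loosely worded sentence. This stands in part. The protocol is not silent; it is inconsistent. But the sentence that creates the obligation is the narrow one, and investigators act on that sentence. The consent form is not part of the text available here and may ask patients to notify the site after treatment; that cannot be excluded, but it would not change what 15.13 obliges the investigator to do.

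On week 0, section 10.1 already requires eligibility to be settled before randomization, and visit 2 has a physical examination and adverse event collection. A pregnancy might therefore come to light without a test, and a patient may report one before week 8. That is fair. Week 8 is the next *scheduled* test, not necessarily the first moment of discovery.

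A reader might infer more than the text supports:

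- *That a conception in the last days of dosing goes unreported.* It does not. The sentence covers a patient or partner who becomes pregnant during treatment, whenever this is discovered. What is lacking is a scheduled contact after week 36 at which it would be detected.
- *That consecutive tests may be 12 + 8 = 20 weeks apart.* This needs the 12-week screening period to apply to each patient. Section 8.1 describes 12 weeks of recruitment and 8.3 gives a 3-month enrollment period, which favors a trial-wide window.
- *That 26/62 = 42% of a risk window is unmonitored.* The protocol names no risk window, and the fraction treats all weeks as equally important. It measures no risk.
- *That the week 0 gap shortens pregnancy reporting.* It does not; the two points are independent.

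**Conclusion.** The point holds as two separate inconsistencies.

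First, the reporting sentence in 15.13 conflicts with the exposure definition in the same section and falls short of the contraception period in inclusion 2. A conception after the last dose and within that period has no explicit reporting duty. The stretch is about 26 weeks for a patient treated to week 36, assuming that 6 months is about 26 weeks and that the duty sentence is read as written.

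Second, the schedule does not carry out what 10.1 and 16.5 require at visit 2. Exclusion 1 rests on a screening test of unstated age, with the next scheduled test 8 weeks into dosing.

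Neither is a matter for a statistical analysis plan: eligibility, visit schedule and pregnancy reporting are protocol content. The documents do not show how many pregnancies would be missed, and no such figure is claimed. The correction is worth making because it is cheap and because the rule, read literally, would miss cases that the protocol itself defines as exposure.

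**What to change.** - **Section 15.13:** reconcile the reporting sentence with the section's own exposure definition and with the contraception period in inclusion 2, for patients and partners, so that all three state one period. Which period is right is for the sponsor to settle.
- **Sections 2 and 8.4:** reconcile the week 0 entries with sections 9.3, 10.1 and 16.5, so that the schedule shows the pregnancy exclusion being confirmed at visit 2 before first dispensing.
- **Sections 11 and 15.2:** tie the Post-Treatment Period and the Follow-Up Period to named visits or dates.

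**Cost.** Wording, and one pregnancy test for women at an existing visit. Some pregnancy reports may also arrive after the database is locked. With last patient out planned for December 2019 and lock for January 2020 (8.3), a 6-month period would run to about June 2020, some 5 months past lock. These reports can be handled as late safety information and need not delay the efficacy analysis.

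The change does not require all serious adverse event and medication collection to be extended by 6 months. That would be a much larger burden across 141 patients, and the inconsistency does not call for it.

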15.14 WITHDRAWAL DUE TO ADVERSE EVENTS

Withdrawal due to adverse event should be distinguished from withdrawal due to Insufficient Response, according to the definition of adverse event noted earlier, and recorded on the appropriate adverse event CRF page.

When a subject withdraws due to a serious adverse event, the serious adverse event must be reported in accordance with the reporting requirements defined below.

15.15 ELICITING ADVERSE EVENT INFORMATION

A consistent methodology of non-directive questioning should be adopted for eliciting adverse event information at all patient evaluation time points.

Examples of non-directive questions include the following:

- "How have you felt since your last clinic visit?"
- "Have you had any new or changed health problems since you were last here?"

15.16 PROCEDURES FOR RECORDING ADVERSE EVENTS

Investigators should use correct medical terminology/concepts when recording adverse events on the Adverse Event CRF. Avoid colloquialisms and abbreviations.

Only one adverse event term should be recorded in the event field on the Adverse Event Form.

15.17 REPORTING REQUIREMENTS

General Instructions

Investigators will seek information on adverse events at each patient contact. All adverse events, whether reported by the patient or noted by study personnel, will be recorded in the patient's medical record and on the Adverse Event Form in CRF.

After prescription of Investigational Product, all adverse events, regardless of relationship to study drug, will be reported.

Each adverse event is to be assessed to determine if it meets the criteria for serious adverse events. If a serious adverse event occurs, expedited reporting will follow local and international regulations, as appropriate.

Reporting of Serious Adverse Event

If a serious adverse event occurs, Sponsor or its representative is to be notified within 24 HOURS OF AWARENESS OF THE EVENT by the investigator or delegate on behalf. In particular, if the serious adverse event is fatal or life-threatening, notification to

Sponsor or its representative must be made IMMEDIATELY, irrespective of the extent of available adverse event information.

This timeframe also applies to additional new information (Follow-Up) on previously forwarded serious adverse event reports as well as to the initial and follow-up reporting of Exposure during pregnancy cases.

In the rare event that the investigator does not become aware of the occurrence of a serious adverse event immediately (e.g., if an outpatient study subject initially seeks treatment elsewhere), the investigator is to report the event within 24 hours after being aware of it and document the time of his/her first awareness of the adverse event.

For all serious adverse events, the investigator is obligated to pursue and provide information to Sponsor or its representative in accordance with the timeframes for reporting specified above. In addition, an investigator may be requested by Sponsor or its representative to obtain specific additional follow-up information in an expedited fashion.

In general, this information will include a description of the adverse event in sufficient detail to allow for a complete medical assessment of the case and independent determination of possible causality. Information on other possible causes of the event, such as concomitant medications and illnesses must be provided. In the case of a subject death, a summary of available autopsy findings must be submitted as soon as possible to Sponsor or its representative or its designated representative.

Reporting of Non-Serious Adverse Event

All Non-Serious Adverse Events will be reported on the adverse event page(s) of the CRF and reported **WITHIN 180 CALENDAR DAYS** to the local regulatory authority.

15.18 INSTRUCTIONS FOR REPORTING SERIOUS ADVERSE EVENTS FOR STUDY TEAM

In the case of occurrence of a SAE, the Investigator must immediately:

1. SEND the signed and dated corresponding page(s) from the CRF to the representative of the monitoring team whose Name, Fax Number and E-mail Address appear on the Study Protocol

2. ATTACH a photocopy of all examinations carried out and the dates on which these examinations were performed. Care should be taken to ensure that the patient's identity is protected and the patient's identifiers in the Clinical Trial are properly mentioned on any copy of source document provided to the Sponsor. For laboratory results, include the laboratory normal ranges;
3. All further documentation should be sent to the Monitoring Team within 1 working day of knowledge. In addition, any effort should be made to further document each SAE that is fatal or life threatening within the week (7 days) following initial notification.

If the **CRA** is Not Available, Please Contact:

Name	[name]
Title	Pharmacovigilance Manager
Mobile	[name]
E-mail	[contact]
Tel	([contact]/2
Fax	([contact]

And sponsor's representative:

Name	[name]
Title	Clinical Research Associate
Mobile	[name]
E-mail	[contact]
Tel	[name]
Fax	([contact]

